14.1 Variables and derivations

Adverse Events (AEs) will be coded using standard GSK dictionary, MedDRA central coding dictionary, version 26.0 or higher.

For the definition of Adverse events (AE) and Serious adverse event (SAE) refer to the protocol section 10.6.

The following parameters will be summarised for the participant's adverse events as mentioned in eCRF:

- Number of participants with at least one AEs pre treatment
- Number of participants with at least one AE during treatment
- Number of participants with at least one AE post treatment
- Number of participants with at least one Drug related AE.
- Number of participants with at least one serious AEs
- Number of participants with at least one Drug related serious AEs
- Number of participants with at least one AESI
- All Adverse Events
- Ongoing AEs
- AEs by Severity
- AEs by Outcome
- AEs by Action Taken with Study treatment
- AEs leading to Death

Derivations:

- The question "Adverse event related to study treatment" is answered "Yes," then respective AEs will be considered as treatment related AE.
- The question "Is the adverse event serious" is answered as "Yes" then respective AE will be considered as serious AEs.
- The question "Is the adverse event serious" is answered as "Yes" and the question "Adverse event related to study treatment" is answered "Yes," then respective AEs will be considered as treatment related SAEs.
- If seriousness criteria are "DEATH" and outcome of adverse event is "FATAL" then we will consider it as AE leading to death.
- Participant's primary reason for discontinuation captured in the eCRF page, study treatment discontinuation is "ADVERSE EVENT" then we will consider it as AE leading to early withdrawal from study.
- Pre- Treatment AEs: AE Start Date < Study Treatment Start Date
- Post- Treatment AE's: AE Start Date > Study Treatment Stop Date

- During Treatment AE's: Treatment Start Date \leq AE Start Date \geq Treatment Stop Date

In section 22 Appendix 2 the algorithm is given for calculation of partial date imputation for Adverse Events, and it will be used for partially missing AE, start and end date imputation.

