14.2 Analysis

Population: Table: ITT

Listing: ITT

Statistics: An overall summary will be presented as the number of participants within each of the event type categories described in the above section, including the incidence of AEs by preferred term (PT) and System organ class (SOC) sorted by decreasing frequency within the SOC & PT. Number and proportion of participants with AEs will be presented. Both number of participants, number of event (One participant may be counted more than once) and percentage will be provided.

The summary of drug related adverse events, serious adverse events, serious drug related adverse events, Adverse Events Leading to Permanent Discontinuation of Study Treatment or Withdrawal from Study and Adverse events of Special interest will be presented by SOC and PT also summary of drug-related AEs by SOC, PT and maximum intensity will be provided.

The most common reported ($\geq 3\%$) AEs and SAEs will be summarized by overall frequency. The Adverse Event will be summarized and presented in data listings using ITT population with all AEs (including coding details SOC and PT only) and participants with SAEs, AESIs, Fatal AEs and events resulting in study discontinuation will be listed separately by participant's number.

Note: If there are uncoded adverse events, then the uncoded category will be added in the AEs by SOC/PT summary tables.

15. Vital Signs

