17.1.2 Primary estimand analyses

Population: Table: ITT

Listing: NA

Statistics:

While on-treatment Policy: Values of the variable up to the time of the intercurrent event.

This strategy summarises the variable while the patient actually receives their randomised treatment. An example of use of this strategy is the standard approach to safety data. Adverse events in efficacy trials are usually summarised over the period while a subject is receiving the randomised treatment.

The primary estimand analysis will be performed for participants experiencing an AE, AESI & SAE while taking treatment. It will follow while on treatment policy. But if a subject discontinues treatment during this period of Visit 2-Visit 4 then values only before discontinuation point will be considered.

Treatment Policy: Actual values of the variable regardless of whether the intercurrent event has occurred.

This approach requires collection of data after the intercurrent event of interest (e.g. continued collection if a patient discontinues treatment) and corresponds to a full ITT approach. If the patient also withdraws from the study, then this becomes a missing data problem. The supplementary estimand analysis will be performed for participants experiencing AE, AESI & SAE while taking treatment and post treatment. It will follow treatment policy.

Summary will be presented as the number of participants experiencing AE, AESI & SAE including the incidence of AEs by alphabetically preferred term (PT) sorted by decreasing frequency within the system organ class (SOC). Number and proportion of participants with AEs will be presented. Both number of participants, number of event (One participant may be counted more than once) and percentage will be provided.

Note: If there are uncoded adverse events, then the uncoded category will be added in the AEs by SOC/PT summary tables.

For the supplementary analysis refer to the SAP section 14.

18. Secondary efficacy estimands

18.1 Change from baseline in trough FEV1 on Day 85 and Day 28

As per the protocol, estimand will be defined as follows:

- **Summary measure:** Mean change from baseline in trough FEV1 on Day 85.
Mean change from baseline in trough FEV1 on Day 28.
- **Population of interest:** COPD patients in India.
- **Key intercurrent events (ICEs):** Discontinuation of treatment.

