21.9 Presentation of visits

- Pre-screen (Visit 0)
- Screen (Visit 1)
- Visit 2
- Visit 3
- Telephonic (Visit 4)
- Visit 5
- Safety follow-up (Visit 6)

22. Appendix 2: Partial date conventions and Concomitant medication guidelines

The whole missing date will not be imputed for this study; only partial date imputation will be performed. Conventions pertaining to partial dates are presented.

Table: Algorithm for partial date imputation

Element	Reporting Detail									
General	
 Partial dates will be displayed as captured in participant listing displays. However, where necessary, display macros may impute dates as temporary variables for sorting data in listings only. In addition, partial dates may be imputed for 'slotting' data to study phases or for specific analysis purposes as outlined below. Imputed partial dates will not be used to derive study day, time to onset or duration (e.g., time to onset or duration of adverse events), or elapsed time variables (e.g., time since diagnosis). In addition, imputed dates are not used for deriving the last contact date in overall survival analysis dataset. 									

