	
 Else if study intervention start date is not missing: 
 If month and year of start date = month and year of study intervention start date, then 
 If stop date contains a full date and stop date is earlier than study intervention start date, then set start date= 1st of month. Else set start date = study intervention start date. 									
Missing start day and month	
 If study intervention start date is missing (i.e. participant did not start study intervention), then set start date = January 1. 									
	
 Else if study intervention start date is not missing: 
 If year of start date = year of study intervention start date, then 									

Element	Reporting Detail						
	
 – If stop date contains a full date and stop date is earlier than study intervention start date, then set start date = January 1. – Else set start date = study intervention start date. 
Else set start date = January 1.
 
 
 Missing end day	A '28/29/30/31' will be used for the day (dependent on the month and year).	
 
 Missing end day and month	No Imputation	
 
 Completely missing start/end date	No imputation	
 
	Missing end day	A '28/29/30/31' will be used for the day (dependent on the month and year).	Missing end day and month	No Imputation	Completely missing start/end date	No imputation
Missing end day	A '28/29/30/31' will be used for the day (dependent on the month and year).						
Missing end day and month	No Imputation						
Completely missing start/end date	No imputation						

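### The SAP's during-treatment AE rule has its second inequality reversed, so as written it selects AEs starting on or after the treatment stop date

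*SAP*

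**What the plan says.** SAP 14.1 sorts AEs by onset date. Pre-treatment means onset before the treatment start date. The post-treatment line is "Post- Treatment AE's: AE Start Date > Study Treatment Stop Date". The during-treatment line is "During Treatment AE's: Treatment Start Date \leq AE Start Date \geq Treatment Stop Date".

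The same section lists this summary row: "Number of participants with at least one AE during treatment". Section 14.2 then commits to the table: "An overall summary will be presented as the number of participants within each of the event type categories described in the above section".

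The primary estimand (SAP 17.1, protocol 9.3.2) is the percentage of participants with an AE, SAE or AESI while taking treatment. SAP 17.1.1 derives only the seriousness and AESI flags. SAP 17.1.2 describes the on-treatment window in words: "But if a subject discontinues treatment during this period of Visit 2-Visit 4 then values only before discontinuation point will be considered". For the treatment-policy version it says: "For the supplementary analysis refer to the SAP section 14".

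SAP section 22 (Appendix 2) imputes partial AE dates. Where the start day is missing and the month is that of treatment start, the usual outcome is "Else set start date = study intervention start date". The exception is an AE whose full stop date precedes treatment. For wholly missing dates it says: "The whole missing date will not be imputed for this study; only partial date imputation will be performed".

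**The concern.** Both comparisons in the during-treatment line make the onset date the later one. The second should bound it from above. As printed, the rule leaves out nearly all on-treatment onsets and takes in every post-treatment onset.

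The direct casualty is the row for AEs during treatment in the overall summary. The primary estimand is exposed as well. Section 17 gives no comparison of AE dates with treatment dates, so the 14.1 line is the only explicit date rule for on-treatment status that a programmer can pick up. Outputs built from all AEs (all-AE, SAE, AESI and treatment-policy summaries) are unaffected. A treatment-policy table built instead as during plus post would lose the same on-treatment onsets, because the union of the two printed rules is again onset on or after stop.

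**Working it through.** **Inputs.** First dose on Day 1 and last dose on Day 84 (protocol 1.1). Safety follow-up on Day 92. Visit 4 window Day 80 to 86 and Visit 6 window Day 91 to 96 (protocol 1.3). Date rules from SAP 14.1. The plan states no figure to reproduce.

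**Reduction.** Write S for treatment start, E for treatment stop and A for AE start. The printed rule is S ≤ A and A ≥ E. Since E ≥ S, A ≥ E already implies A ≥ S, so the rule is simply A ≥ E. A check over a grid of start, stop and onset days with E ≥ S found no exception.

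**Day-by-day classification**, with pre: A < S; during as printed: A ≥ E; post: A > E.

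| Case | Stop day | Last follow-up day | On-treatment days meeting the rule | Days in no category | Days both during and post |
|---|---|---|---|---|---|
| Completer, scheduled days | 84 | 92 | 1 of 84 | 83 (1–83) | 8 (85–92) |
| Completer, early end of windows | 80 | 91 | 1 of 80 | 79 (1–79) | 11 (81–91) |
| Completer, late end of windows | 86 | 96 | 1 of 86 | 85 (1–85) | 10 (87–96) |
| Early discontinuer (assumed stop day) | 28 | 92 | 1 of 28 | 27 (1–27) | 64 (29–92) |

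For the scheduled completer, 1/84 = 1.2% of on-treatment days meet the rule and 83/92 = 90% of observed days have no category. Day 84 is the only treatment day classified correctly.

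**Partial dates.** An onset imputed to Day 1 with stop on Day 84 gives: pre, 1 < 1, false; during as printed, 1 ≥ 84, false; post, 1 > 84, false. An AE that the imputation rule places at treatment start therefore falls in no category.

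**Corrected rule.** With S ≤ A ≤ E, every onset day falls in exactly one of pre, during and post, in all the cases above and over the whole grid.

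**Illustration of size.** The documents give no AE rate or onset pattern. Assume a Poisson count of r AEs per participant over 84 days, with uniform onset and the same daily rate to Day 92. Incidence over d days is 1 − exp(−r·d/84). The intended window has d = 84. The printed rule covers Days 84–92, so d = 9.

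| Assumed r | Intended (d = 84) | As printed (d = 9) | Of 229 participants |
|---|---|---|---|
| 0.20 | 18.1% | 2.1% | about 42 against 5 |
| 0.35 | 29.5% | 3.7% | about 68 against 8 |
| 0.50 | 39.3% | 5.2% | about 90 against 12 |

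These incidences show scale only. The finding rests on the day counts.

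**The case against.** The strongest reply is that this is an evident slip with one row at stake. The pre and post lines beside it are correct, and their complement is exactly start ≤ onset ≤ stop, so the meaning can be recovered from date rules alone. Section 17.1.2 sends only the supplementary analysis to section 14. For the primary analysis it gives its own window by visit and discontinuation point, which can be programmed without 14.1. A literal program would also leave most AEs unclassified, which should show up against the all-AE row of the same table. Finally, the text was read from PDF, and the sign may have been misread.

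Much of this stands. The intent is not in doubt, the primary table does not necessarily inherit the error, and a wrong published count is possible but not shown to be likely. It does not rescue the line. A derivation in the SAP is what programmers and validators work to, and this one feeds a planned output. The compliance bands in SAP 11.1 come through with both signs sensible, so a misreading is not the default explanation, though the original page should be checked. Nor does the prose settle the boundary. Read strictly, values before the discontinuation point exclude an AE starting on the stop date, whereas the general description in 17.1.2, up to the time of the intercurrent event, can be read to include it.

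**Conclusion.** The concern holds: the during-treatment rule in SAP 14.1 is wrong as written. For a completer on the scheduled days it captures 1 of 84 on-treatment onset days, leaves 83 days unclassified and counts 8 days twice. These figures need only the planned dosing and follow-up days and the printed sign. The certain effect is on the row for AEs during treatment, if it is programmed literally. The effect on the primary while-on-treatment table is conditional on the same flag being used there. It should be corrected, but it is an error in a written rule and not a reason to change the analysis.

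**What to change.** 1. In SAP 14.1, after checking the symbol on the original page, define during-treatment AEs as study treatment start date ≤ AE start date ≤ study treatment stop date.
2. Cite that rule in SAP 17.1.1 or 17.1.2 as the on-treatment flag for the primary estimand.
3. Reword the discontinuation-point sentence in 17.1.2 so that it treats the stop date as 14.1 does.
4. State in which row AEs with a wholly missing start date appear, since these are not imputed. The three categories are exclusive and exhaustive only where the AE start date is known or imputed and the treatment start and stop dates are known.
5. Confirm that the programmed flag matches the corrected rule.

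The cost is one line in 14.1, a cross-reference and a wording change in 17.1, a short statement on missing dates and a program check. No protocol amendment and no new data are needed.

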14.2 Analysis

Population: Table: ITT

Listing: ITT

Statistics: An overall summary will be presented as the number of participants within each of the event type categories described in the above section, including the incidence of AEs by preferred term (PT) and System organ class (SOC) sorted by decreasing frequency within the SOC & PT. Number and proportion of participants with AEs will be presented. Both number of participants, number of event (One participant may be counted more than once) and percentage will be provided.

The summary of drug related adverse events, serious adverse events, serious drug related adverse events, Adverse Events Leading to Permanent Discontinuation of Study Treatment or Withdrawal from Study and Adverse events of Special interest will be presented by SOC and PT also summary of drug-related AEs by SOC, PT and maximum intensity will be provided.

The most common reported ($\geq 3\%$) AEs and SAEs will be summarized by overall frequency. The Adverse Event will be summarized and presented in data listings using ITT population with all AEs (including coding details SOC and PT only) and participants with SAEs, AESIs, Fatal AEs and events resulting in study discontinuation will be listed separately by participant's number.

Note: If there are uncoded adverse events, then the uncoded category will be added in the AEs by SOC/PT summary tables.

15. Vital Signs

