Serious cardiovascular events	
Cardiovascular (CV) effects are a potential class effect associated with anti-muscarinic and beta agonist therapies.
 
In the COPD population, there is a high prevalence of concurrent CV disease and the prevalence of CV co morbidities increases with worsening severity of COPD.
 
In study CTT116855 (also designated a category 3 safety study, as requested by the EU CHMP), for the Cardiovascular (CV) effects AESI, there were similar incidences and exposure adjusted rates across the FF/UMEV/VI, FF/VI and UMEC/VI treatment groups (10% to 11% and 157.0 to 167.2, respectively). In the Major adverse cardiac events (MACE) analysis 2% in the FF/UMEV/VI group, 1% in the FF/VI group, and 2% in the UMEC/VI group reported any MACE).
	
 - Participants will be informed about the risk in the informed consent. - Investigators are informed of the risk in the IB. - Appropriate exclusion criteria as specified in Section 5.2 of the protocol, including - Electrocardiogram (ECG) inclusion criteria - Vital sign assessments (heart rate and blood pressure) as per protocol. - Protocol defined stopping criteria as per Section 7.1.2.

Potential Risk of Clinical Significance	Summary of Data/Rationale for Risk	Mitigation Strategy
	
There were no emerging safety signals based on review of the vital signs, ECGs and Holter data (where performed) across FF/UMEV/VI clinical development studies to date.
 
The effect of FF/UMEV/VI on the QT interval has not been evaluated in a thorough QT (TQT) study. TQT studies for FF/VI and UMEC/VI did not show clinically relevant effects on QT interval at clinical doses of FF, UMEC and VI.
	
Adrenal suppression	
Oral corticosteroids are known to influence the hypothalamic-pituitary-adrenal (HPA) axis leading to a reduction in cortisol production. Due to the low dose and low systemic exposure with ICSs, this potential effect is not clear, nor is the possible impact of any change in cortisol.
 
In study CTT116855, no events were reported in the adrenal suppression AESI group for FF/UMEV/VI.
 
With respect to the FF/VI clinical development program, a formal HPA study and multiple studies with COPD (and asthma) participants monitored urinary
	
-Investigators are informed of the risk in the IB

Potential Risk of Clinical Significance	Summary of Data/Rationale for Risk	Mitigation Strategy

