8.3.4. Adverse events of special interest

Within the FF, UMEC, and VI clinical development programs for asthma/COPD, the following ICS, LAMA, and LABA class effects were considered adverse events of special interest (AESIs) ([Table 4](#)).

Table 4 Adverse Events of Special Interest (AESI) Definitions

Special interest group	Special interest subgroup	PTs/SMQs for inclusion
CV effects	Cardiac arrhythmia	Cardiac arrhythmia (SMQ), excluding congenital and neonatal arrhythmias
	Cardiac failure	Cardiac failure (SMQ)
	Cardiac ischemia	Ischemic Heart Disease (SMQ)
	Stroke	CNS haemorrhages and cerebrovascular conditions (SMQ)
	Hypertension	Hypertension (SMQ)
Pneumonia ¹	Pneumonia	Infective pneumonia (SMQ)
LRTI (excluding infective pneumonia SMQ)		Selected PTs
Decreased BMD and associated fractures		Osteoporosis/osteopenia (SMQ) Selected PTs
Hypersensitivity		Hypersensitivity (SMQ) Angioedema (SMQ) Anaphylactic reaction (SMQ)
Anticholinergic syndrome		Anticholinergic Syndrome SMQ
Gastrointestinal obstruction		Gastrointestinal obstruction SMQ
Adrenal suppression		Selected PTs
Antimuscarinic ocular effects/corticosteroid-associated eye disorders	Glaucoma (antimuscarinic/corticosteroid)	Glaucoma (SMQ)
	Cataracts (corticosteroids)	Lens disorder (SMQ)

Special interest group	Special interest subgroup	PTs/SMQs for inclusion
Effects on glucose		Hyperglycaemia/ new onset diabetes mellitus (SMQ)
Local steroid effects		Selected PTs
Urinary retention		Selected PTs
Effects on potassium		Selected PTs
Tremor		Selected PTs
Asthma/bronchospasm for asthma-related intubations and deaths		Asthma/bronchospasm SMQ
Dry mouth/drying of airway secretions		Selected PTs (narrow and broad focus) ²

Abbreviations: BMD, bone mineral density; CNS, central nervous system; CV, cardiovascular; LRTI, lower respiratory tract infection; PT, preferred term; RAP, Reporting and Analysis Plan; SMQ, standardized MedDRA queries.

1. All diagnosed pneumonias (with or without radiographic confirmation) were to be recorded on the adverse event page of the eCRF and on the pneumonia page of the eCRF. All suspected pneumonias were required to be confirmed by the presence of new infiltrates on a posteroanterior and lateral chest x-ray (≤ 48 h of suspected event) (details provided in Protocol Section 7.5.1.6).
2. Includes nasopharyngitis.

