1.1 Introduction

The purpose of this Statistical Analysis Plan (SAP) is to provide details of the statistical analyses that have been outlined within the Protocol Amendment No. 4 for 212655 dated 03 May 2023. The scope of this plan includes the final analysis, which will be executed by the Biostatistics department unless otherwise specified. Any post-hoc or unplanned analyses performed but not described in this SAP will be clearly described in the CSR.

2. Trial objectives

The following objectives are those stated in the protocol.

Objectives	Estimands/ Endpoints
Primary	

 To evaluate the safety profile of FF/UMEV/VI over 12 weeks in patients from India 	
The primary Estimand is defined by the following:
 
 Endpoint: incidence of adverse events (AE), serious adverse events (SAE) and adverse events of special interest (AESIs). Summary number and percentage of participants experiencing an AEs, SAEs and number and percentage of participants experiencing AESIs by system organ class and by preferred term. Population of interest: COPD patients in India. Key intercurrent events: discontinuation of treatment Strategy for intercurrent events: a While on Treatment strategy will be used for treatment discontinuation. This estimates the percentage of participants experiencing an AE or SAE while taking treatment. Participants that test positive for COVID-19 will immediately discontinue study treatment. Therefore COVID-19 will be included as the intercurrent event of study treatment discontinuation and will be handled with While on Treatment strategy for the primary estimand. A supplementary estimand will be defined using identical properties as for the primary estimand (summary measure, population of interest and key intercurrent events), however this supplementary estimand will report all AEs regardless of the discontinuation of study treatment.

[figure not shown]
	
• Endpoints:
• Incidence of AEs, SAEs and AESIs• Strategy for intercurrent events:
• Treatment policy strategy will be used for treatment discontinuation. This summary will therefore be inclusive of all on-treatment and post-treatment AEs.
Secondary	

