17.1.1 Variables and derivations

For the definition of Adverse events (AE) and Serious adverse event (SAE) refer to the protocol section 10.6.

Derivations:

- The question “Is the adverse event serious” is answered as “Yes” then respective AE will be considered as serious AEs.
- The question “Is this event an adverse event of special interest (AESI)” is answered as “Yes” then respective AE will be considered as AESI.

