21.4.3 Frequencies and percentages [n, (m) and %]

Percent values should be reported inside parentheses with percent symbol, no blank spaces are included within the parentheses, e.g., "(25%)." percentages greater than 0 and less than 1 as "<1%" and those greater than 99 and less than 100 as ">99%". Percentages exactly equal to 0% will be shown as blanks in the table. So, counts of 0 will be presented as 0 and not as 0 (0%).

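### AESIs are a primary endpoint component, but no planned table counts participants by the special-interest groups that define them

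*SAP*

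**What the plan says.** AESI incidence is part of the primary endpoint, with AEs and SAEs (Protocol 3; SAP 2 and 17.1).

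- **Definition.** Table 4 in Protocol 8.3.4 lists 16 special-interest groups, each built from standardised MedDRA queries (SMQs), selected preferred terms, or both. CV effects has five subgroups: arrhythmia, failure, ischaemia, stroke and hypertension.
- **Known profile.** Protocol 2.3.1 reports the 52-week study by these groups. For example, "for the Cardiovascular (CV) effects AESI, there were similar incidences and exposure adjusted rates" across its three arms: 10% to 11%, and 157.0 to 167.2. Pneumonia on the study treatment was 8%, or 95.8 per 1,000 participant-years. Hypersensitivity (5%), anticholinergic syndrome (4%) and decreased bone mineral density (2%) are given in the same way.
- **Summary measure.** The estimand in Protocol 3, repeated in SAP 2 and 17.1, asks for "number and percentage of participants experiencing AESIs by system organ class and by preferred term". Protocol 9.3.2 asks only for an overall AESI figure.
- **Planned outputs.** SAP 14.1 has one row, "Number of participants with at least one AESI". SAP 14.2 says "Adverse events of Special interest will be presented by SOC and PT" and adds a separate listing of participants with AESIs.
- **Identification.** SAP 17.1.1 takes AESI status from a yes/no question on the eCRF. The SAP does not cite Table 4 or the SMQs and specifies no group variable.

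**The concern.** The definition and the reporting use different units. An AESI group is a clinical question: did participants have cardiovascular events, pneumonia, or ocular effects? A table by body system and preferred term does not answer it, and a single any-AESI total pools groups with nothing in common.

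The trial has one arm and no hypothesis test (Protocol 9.1), so a reader can judge the safety profile only against what is already known. The protocol states what is known by group. For a primary endpoint component, the plan yields no pre-specified figure in that unit, and any group count would be assembled after the data are seen.

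**Working it through.** **1. The plan's own figure.** Protocol Table 5 gives the chance of seeing at least one participant with an event of risk 1/100 when N = 220. 1 − 0.99^220 = 0.8904, as stated. The plan gives no expected count for any AESI group.

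**2. Planned outputs against the group count.**

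| Output | Gives participants per Table 4 group? |
|---|---|
| Any-AESI row (SAP 14.1) | No, all groups are pooled |
| AESIs by SOC and PT (SAP 14.2, 17.1) | No, rows carry no group label, and a participant with two terms is in two rows, so rows do not add up to participants |
| AESI listing (SAP 14.2) | Only by hand, using a group assignment that the SAP does not define |

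**3. Size of a group row at the known level.** Inputs: N = 229 to be treated (Protocol 9.2), since the AE tables use the ITT population; 12 of 52 weeks; the CV and pneumonia figures above. Two scalings are used, both with a constant hazard. The CV rate has no stated unit; it is taken as per 1,000 participant-years, as for pneumonia.

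From the rate, risk = 1 − exp(−rate × 12/52):
- CV at 157.0: 0.1570 × 12/52 = 0.0362; risk 3.56%; 229 × 0.0356 = 8.1 participants.
- CV at 167.2: 0.1672 × 12/52 = 0.0386; risk 3.78%; 8.7 participants.
- Pneumonia at 95.8: 0.0958 × 12/52 = 0.0221; risk 2.19%; 5.0 participants.

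From the incidence, risk = 1 − (1 − p)^(12/52):
- CV at 10%: 2.40%; 5.5 participants.
- CV at 11%: 2.65%; 6.1 participants.
- Pneumonia at 8%: 1.91%; 4.4 participants.

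So the expected rows are about 5.5 to 8.7 participants for CV effects (2.4% to 3.8%) and 4.4 to 5.0 for pneumonia (1.9% to 2.2%). The two scalings differ because the quoted rate and incidence do not match under a constant hazard: a rate of 157.0 implies 1 − exp(−0.157) = 14.5% over a full year, against the quoted 10% to 11%. Repeat events or incomplete follow-up could explain this; the documents do not say.

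**4. What a group row would show.** Clopper-Pearson 95% intervals, N = 229:
- 8 participants: 3.5% (1.5 to 6.8), near the known level.
- 11 participants: 4.8% (2.4 to 8.4), double the low end.
- 17 participants: 7.4% (4.4 to 11.6), double the high end.

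**5. What the SOC rows would show.** Two participants are 2/229 = 0.87%, printed as <1% under SAP 21.4.3; three are 1.31%, printed as 1%. For 11 to 17 participants to leave every SOC row at two or fewer, they would have to fall in at least 11/2, rounded up to 6, or 17/2, rounded up to 9, different SOCs. A doubling would therefore normally lift some SOC row to 1% or more. That row still would not be the group figure, because it may also hold AESIs from other groups and may miss part of this one.

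**The case against.** The strongest reply is that the protocol chose this measure. Its estimand names SOC and PT, and the SAP implements that. No section plans a formal comparison with the 52-week study, whose figures appear as risk background. The AESI listing would let someone assign about eight CV participants to groups by hand. The output templates (SAP 8) are a separate document and may already hold a group-level shell. All of this stands. It makes the point a gap in both documents and not a SAP departure, but it does not supply a pre-specified group count.

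Three stronger readings are tempting and are not supported:

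- *A group excess disappears into rows printed as <1%.* SAP 21.4.3 does show "percentages greater than 0 and less than 1 as" <1%, and single PT rows could well be that small. But participant and event counts are printed beside the percentages, and SOC rows partly aggregate the terms (step 5).
- *Common colds inflate the any-AESI total.* A Table 4 footnote to the dry-mouth group says "Includes nasopharyngitis". But the SAP flags AESIs by an eCRF question, not by Table 4, and the documents give no rate for nasopharyngitis, so no size can be put on this.
- *Group rows alone would make the results comparable.* They would not. The quoted percentages cover 52 weeks, and a 12-week percentage set beside them would look falsely reassuring. A rate per participant-year is also needed.

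**Conclusion.** The point holds as a reporting gap. A primary endpoint component is defined in 16 groups, its known profile is quoted in those groups, and no planned table reports it in them. The group count cannot be summed from the planned rows and can be recovered only by unplanned hand work on the listing.

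The counts at stake are small but readable: about 5.5 to 8.7 CV-effects participants of 229, and 4.4 to 5.0 with pneumonia, if India resembles the 52-week study. These figures assume a constant hazard, full 12-week exposure, the rate unit stated above and a population of similar risk. The finding itself needs none of these assumptions; it rests on what the tables contain. It does not imply that the SAP breaches the protocol, or that a safety excess would go unseen.

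**What to change.** In SAP 14.2 and 17.1.2, add an AESI table by Table 4 group and subgroup, with PTs nested inside, for both the on-treatment and the treatment-policy summaries. For each group and subgroup give participants, percentage, events, 95% confidence interval and exposure-adjusted rate per 1,000 participant-years. State whether the rate counts events or participants. For the on-treatment rate, the exposure duration in SAP 11.1 can serve as denominator; the treatment-policy rate needs follow-up time as well.

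Assign group membership from the Table 4 SMQs, and fix the list of selected PTs before database lock. Eight of the 16 groups depend wholly or partly on such lists, which neither document gives.

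Keep the SOC/PT table as the protocol's stated measure. Record the addition in SAP section 4, or align the estimand wording in both documents. If the output templates already hold such a table, the SAP text need only name it.

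Cost: one more display and the PT mapping work. No new participant data are needed.
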